6. DOSING DELAYS/DOSE MODIFICATIONS

Dose Modifications for cisplatin, days 8 and beyond

Dose Level	Every 3-week Cisplatin	Weekly Cisplatin
-2	50 mg/m ² every 3 weeks	20 mg/m ² weekly
-1	75 mg/m ² every 3 weeks	30 mg/m ² weekly
0	100 mg/m ² every 3 weeks	40 mg/m ² weekly

No more than two dose reductions are allowed and no re-escalation of dosing is allowed. If a subject requires more than two dose reductions, cisplatin will be permanently discontinued. Every effort will be made to complete all planned doses of chemotherapy, with dose modifications listed below, however, no chemotherapy will be given after completion of radiation.

Neutropenia. If on the day of scheduled treatment with cisplatin the absolute neutrophil count (ANC) is < 1000, hold treatment until ANC ≥ 1000 then treat at 100% dose.

Neutropenic fever. If grade 3 or 4 neutropenic fever occurs, defined as temperature ≥38.5°C [101°F] sustained for more than one-hour concomitant with ANC <500/mm³, hold cisplatin until ANC >1000, and reduce subsequent cisplatin doses by 1 dose level.

Thrombocytopenia. If on the day of scheduled treatment with cisplatin the platelet count is <75,000 hold treatment until platelets are >75,000 then treat at 100% dose.

Thrombocytopenia that results in significant bleeding. If grade 3 or 4 thrombocytopenia occurs with bleeding that is clinically significant, as determined by the treating physician, hold cisplatin until platelets are >75,000 and reduce subsequent cisplatin doses by 1 dose level.

Neurotoxicity. If grade 3 or greater neurotoxicity, including neuropathy occurs, hold cisplatin until resolution to less than or equal to grade 1. Resume cisplatin at one dose level lower. If grade 3 or greater neurotoxicity persist after two dose reductions or does not improve after 14 days, discontinue cisplatin.

Renal Toxicity. If a subject's creatinine clearance falls below 50 ml/min, cisplatin should be held for that dose and should only be restarted once the creatinine clearance improves to >50 ml/min. Subsequent doses should be dose reduced by one dose level. If Cr Cl does not recover to >50 ml/min after 14 days, discontinue cisplatin.

Mucositis: If grade 4 mucositis occurs, hold cisplatin until resolution to less than or equal to grade 2 and reduce subsequent cisplatin doses by 1 dose level.

Ototoxicity or tinnitus: If grade 3 or greater ototoxicity or tinnitus occurs, hold cisplatin until resolution to less than or equal to grade 2 and reduce subsequent cisplatin doses by 1 dose level. If grade 3 or greater hearing loss or tinnitus persist after two dose reductions or does not improve after 14 days, discontinue cisplatin.

Dose Modifications for Other Toxicity: In the event of any other (except nausea and vomiting) grade 3 or 4 non-hematologic toxicity not discussed above, hold all protocol treatment and discuss with the PI. For treatment or dose modification related questions, please contact the PI.

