5.2.2 Cisplatin Dosing

Use the actual body weight as long as the BSA is ≤ 2.3 . If the BSA is > 2.3 , recalculate using the adjusted body weight, and use the recalculated BSA to determine the dose with no cap.

Estimate Ideal body weight in (kg)

Males: IBW = 50 kg + 2.3 kg for each inch over 5 feet

Females: IBW = 45.5 kg + 2.3 kg for each inch over 5 feet

Adjusted body weight

$$AjBW = IBW + 0.4(ABW - IBW)$$

Arm 1 – Conventional fractionation plus every 3-week cisplatin

Patients will receive cisplatin (100 mg/m²) administered intravenously over 1 hour on days 1, 22, and 43 of the treatment course, relative to the initiation of radiation.

Arm 2 – Conventional fractionation plus weekly cisplatin

Patients will receive cisplatin (40 mg/m²) administered intravenously over 1 hour on days 1, 8, 15, 22, 29, 36, and 43 of the treatment course, relative to the initiation of radiation.

Premedication: Arms 1 & 2

Suggested premedication: include aprepitant (intravenous or oral), ondansetron, dexamethasone and either promethazine or prochlorperazine, per institutional standard. This trial endorses the NCCN guidelines for anti-emetic prophylaxis.

Pre- and Post-hydration: Arms 1 & 2

Patients must receive vigorous hydration and diuresis. A suggested regimen is: pre-hydration with a 1 liter of normal saline with electrolyte supplementation (e.g. potassium, magnesium) per standard of care, over 2 hours i.v. immediately prior to cisplatin. Then cisplatin 100 mg/m² in 500 ml normal saline is administered over 1 hour. Following cisplatin infusion, an additional 1 liter of normal saline with electrolyte supplementation (e.g. potassium, magnesium) per standard of care, given post-hydration over 2 hours.

Please see Section 6.0 for all dose modifications of cisplatin.

5.3 **Radiation Therapy**

All radiation therapy is considered standard of care, and toxicities and dose modifications will be made by the treating physician based on institutional standards. The guidelines below are recommended practice but may be modified at the discretion of the treating radiation oncologist.

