5.3.1 Dose Specifications

IMRT has been a standard of care in the U.S. beginning in 2005 and is now widely used in practice. Use of H&N IMRT in RTOG protocols (and associated QA) was begun in 2005 in RTOG 0522, as an optional technique. At the close of the accrual phase, approximately 90% of cases enrolled on 0522 (>800 patients) were treated with IMRT. Oropharynx cases comprised 70% of the study population.

IMRT will be delivered in 30-35 fractions over 6-7 weeks, 5 fractions weekly. The primary tumor and involved nodes (CTV1) will typically consist of a 0.5-1.5 cm expansion of the gross tumor volume (GTV) to cover potential local invasion and will be prescribed 2 Gy/fraction, total 55-70Gy. High-risk sub-clinical disease sites, which include possible local subclinical infiltration at the primary site (primary site CTV2) and first echelon nodes, which are not clinically or radiographically involved (nodal CTV2), should be expanded by 3-5 mm to create PTV2. PTV2 should receive 1.6 Gy/fraction to a total dose of 52.8 Gy to 56 Gy. Lower-risk targets (PTV3) (such as neck nodal levels which are not first echelon nodes and are not adjacent to levels containing grossly involved nodes) will be prescribed 50-52.5 Gy. If the low neck is treated, the preferred technique is to treat with isocentric matching AP or AP-PA fields with larynx block, matched to the IMRT portals just above the arytenoids. The dose will be 2 Gy per fraction prescribed to 3 cm depth to a total dose of 50 Gy in 25 daily fractions. Whole-neck IMRT is allowed. This can be achieved by either boosting the low neck field with an additional 16 Gy in 8 fractions, by an AP or AP-PA fields, or by planning the whole neck using IMRT. In cases of gross involvement of the vallecula or low neck, whole-neck IMRT should be considered. Whole-neck IMRT may also be considered if level VI is considered to be at risk due to gross involvement of level IV nodes. All plans must be normalized such that 95% of the volume of the PTV is covered with prescription dose.

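### An unbroken 30-fraction radiation course ends by day 42, so the day-43 cisplatin dose collides with Section 6; with Section 6 applied, these patients' maxima are 200 v 240 mg/m², not 300 v 280

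*Combined protocol and SAP*

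**What the plan says.** **Cisplatin schedule.** Section 5.2.2 gives Arm 1 100 mg/m² on days 1, 22 and 43, and Arm 2 40 mg/m² on days 1, 8, 15, 22, 29, 36 and 43. Both are counted from the start of radiation. Section 10 shows the last dose in week 7 for both arms. Section 5.2.1 describes all 3 or 7 doses as given in the course of radiation, tabulates maximum cumulative doses of 300 and 280 mg/m², calls the arms similar in cumulative dose, and aims for at least 200 mg/m² in every patient. It lets cisplatin and radiation start one day apart.

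**Radiation course.** Section 5.3.1 states: "IMRT will be delivered in 30-35 fractions over 6-7 weeks, 5 fractions weekly". Section 5.3 qualifies this: "The guidelines below are recommended practice but may be modified at the discretion of the treating radiation oncologist". Section 5.5 gives a treatment duration of 7 weeks in the absence of delays for adverse events.

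**Limit on chemotherapy.** One sentence in Section 6 opens with "Every effort will be made to complete all planned doses of chemotherapy" and then, after a contrasting however, closes with "no chemotherapy will be given after completion of radiation".

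**Infusion text.** The suggested hydration regimen in 5.2.2, under a heading that covers both arms, describes infusing cisplatin at 100 mg/m². Arm 2 is assigned 40 mg/m² in the same section and in 5.2.1, Section 6 and Section 10.

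**The concern.** For a course length that 5.3.1 itself names, the schedule asks for a dose that Section 6 rules out and that cannot fall within radiation as 5.2.1 describes. Losing the day-43 dose costs the arms unequal amounts: 100 of 300 mg/m² (33%) in Arm 1 and 40 of 280 mg/m² (14%) in Arm 2. In these patients the arm with the higher planned total becomes the arm with the lower one.

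The primary endpoint compares cisplatin-related toxicity between the arms over 90 days, and the similarity of cumulative dose is part of how 5.2.1 presents that comparison. Instructions on a dose inside that window should not conflict, and the description of planned exposure should hold for every course length that the protocol names.

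**Working it through.** **1. Reproduce the stated maxima.** 3 × 100 = 300 mg/m² and 7 × 40 = 280 mg/m². Both match the table in 5.2.1.

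**2. Find the last radiation day.** Inputs from 5.3.1: 30 to 35 fractions, 5 per week. Assumptions: weekday treatment, no breaks, day 1 = first fraction. Let k be the start weekday (Monday = 0 to Friday = 4), n the number of fractions and m = k + n − 1. Then

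last day = 7 × floor(m/5) + (m mod 5) − k + 1.

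For n = 30 and a Monday start, m = 29 and the last day is 35 + 4 − 0 + 1 = 40. For a Tuesday start, m = 30 and the last day is 42 + 0 − 1 + 1 = 42. All cases:

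| Fractions | Mon | Tue | Wed | Thu | Fri | Day 43 within the course? |
|---|---|---|---|---|---|---|
| 30 | 40 | 42 | 42 | 42 | 42 | No |
| 31 | 43 | 43 | 43 | 43 | 43 | Yes |
| 32 | 44 | 44 | 44 | 44 | 46 | Yes |
| 33 | 45 | 45 | 45 | 47 | 47 | Yes |
| 34 | 46 | 46 | 48 | 48 | 48 | Yes |
| 35 | 47 | 49 | 49 | 49 | 49 | Yes |

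Within the stated range, only 30 fractions are affected: day 43 falls 1 to 3 days after the last fraction. If one fraction is missed and added at the end, as 5.3.2 permits, the 30-fraction course ends on day 43 for every start weekday and the conflict disappears.

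**3. Apply Section 6 to the 30-fraction course.**
- Arm 1: days 1 and 22 remain, 2 × 100 = 200 mg/m².
- Arm 2: days 1 to 36 remain, 6 × 40 = 240 mg/m².
- Arm 1 minus Arm 2: 300 − 280 = +20 as stated; 200 − 240 = −40 here.
- Margin over the 200 mg/m² aim: 0 in Arm 1 and 40 in Arm 2.

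**4. Check the one-day start window.** Section 5.2.2 counts cisplatin days from radiation, so as written the window does not move day 43. If a cisplatin start one day early were carried through, the last dose would fall on radiation day 42. That is within a 30-fraction course for Tuesday to Friday starts (last day 42) but not for Monday starts (last day 40).

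**5. Compare the other figures in 5.3.1.**
- CTV1 "will be prescribed 2 Gy/fraction, total 55-70Gy": 60/2 = 30 and 70/2 = 35 fractions, so a 60 Gy total fits a 30-fraction course.
- "PTV2 should receive 1.6 Gy/fraction to a total dose of 52.8 Gy to 56 Gy": 52.8/1.6 = 33 and 56/1.6 = 35 fractions.
- Low neck, "to a total dose of 50 Gy in 25 daily fractions", with the option of "boosting the low neck field with an additional 16 Gy in 8 fractions": 25 + 8 = 33 fractions.

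**The case against.** **Section 6 already settles it.** The limiting clause qualifies the effort to give all planned doses, and 5.2.1 agrees by placing the doses within radiation. This largely stands. A reader might infer that the protocol leaves the day-43 dose wholly open, with two equally good readings. The text does not support that: only the section title, on delays and modifications, hints that the clause is confined to delayed doses. What remains is that 5.2.2 and Section 10 schedule the dose without exception, and 5.2.1 draws its table and similarity statement from that full schedule.

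**A maximum is only a ceiling.** This is correct. A reader might infer that 300 and 280 are wrong, but they reproduce exactly and stay true as ceilings. The documents also set no threshold for similar doses. The narrower point survives: for these patients the ceilings cannot be reached if Section 6 is followed, and the order of the arms reverses.

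**The trigger is narrow.** This is also correct. It needs 30 fractions and no break. The 7 weeks in 5.5, the calendar, and the PTV2 and boosted low-neck figures point to longer courses, and the radiation text is modifiable. None of this removes the 30 fractions and 6 weeks named in 5.3.1. The 25 fractions there belong to a low-neck field and do not show a shorter IMRT course.

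**No trial-level harm is shown.** Agreed. A reader might infer that the arms become unequal overall, or that the toxicity comparison or power suffers. With an assumed share s of affected patients, equal in both arms, the mean maxima are 300 − 100s and 280 − 40s, a gap of |20 − 60s|. This is 14 mg/m² at s = 0.10, 0 at s = 1/3 and 10 at s = 0.50. It exceeds the stated 20 only if s is above 2/3. The documents do not give s.

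**The infusion text is only a suggestion.** True, and the arm doses are stated clearly nearby, so it does not show that 100 mg/m² was intended for Arm 2. The text still contradicts the assigned dose.

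**Conclusion.** The inconsistency is real and limited. For an uninterrupted 30-fraction course, the scheduled day-43 dose falls after radiation, contrary to 5.2.1 and Section 6. On the plain reading of Section 6, the attainable maxima are 200 mg/m² (Arm 1) and 240 mg/m² (Arm 2), against the stated 300 and 280, so the unqualified similarity statement does not describe these patients.

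This rests on weekday treatment at five fractions per week, no breaks, and cisplatin days counted from radiation as 5.2.2 states. It is a point about individual patients. From 31 fractions the stated maxima are attainable, and an early cisplatin start carried through could remove the conflict for some patients. No effect on toxicity rates or power is claimed.

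The 100 mg/m² in the infusion text for both arms is a separate contradiction. Both should be fixed because they concern dosing instructions in a trial that compares cisplatin toxicity between schedules. Which dose or rule should apply is not a question for this review.

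**What to change.** - Reconcile 5.2.1, 5.2.2, 5.3.1, 5.5, Section 6 and Section 10 so that one rule, chosen by the investigators, covers the day-43 dose when radiation has already ended.
- State whether the Section 6 limit covers scheduled doses as well as delayed ones, and whether the one-day start window shifts later cisplatin days.
- Qualify the maximum-dose table and the similarity statement in 5.2.1 by course length.
- Reconcile the infusion text for both arms in 5.2.2 with the arm-specific doses.

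The cost is a wording amendment. It needs no extra patients, visits, tests or data fields.

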5.2 Cisplatin Administration

Treatment will be administered on an inpatient or outpatient basis. Reported adverse events and potential risks are described in Section 7. Appropriate dose modifications are described in Section 6. No investigational or commercial agents or therapies other than those described below may be administered with the intent to treat the patient's malignancy.

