5.2.1 Planned Treatment

Treatment will consist of standard of care radiation therapy to the primary tumor of the head and neck and involved nodal metastasis and draining nodal basin, as determined by treating radiation oncologist. Patients will be randomized to receive cisplatin at 100 mg/m² every 3 weeks (3 doses) during radiation versus cisplatin at 40 mg/m² once weekly (7 doses) during radiation. This will provide similar cumulative doses of cisplatin in all arms of the study.

Cisplatin Arm	Maximum Cumulative Dose
Every 3 weeks	300 mg/m ²
Weekly	280 mg/m ²

According to a recent review, total doses above 200 mg/m² during radiation lead to higher overall survival [17], and every attempt will be made to reach at least 200 mg/m². Because of the significant differences in response to therapy in oropharyngeal carcinoma (OPC) due to human papilloma virus (HPV) infection, HPV status will be recorded at baseline and adjusted during final analyses where appropriate.

Patients will first be designated by the enrolling CRA, in conjunction with the enrolling physician, as either: a) Cohort 1 (locally advanced non-nasopharyngeal SCCHN that is unresectable) OR b) Cohort 2 (resected and at high risk of recurrence with at least one of the following criteria: extracapsular nodal extension, or invasive cancer at the primary tumor resection margin (positive margin), lymphovascular invasion or perineural invasion, pT3 or pT4 primary, or the presence of multilevel nodal disease. Subjects will then be randomized to receive either Arm 1 or Arm 2 cisplatin as below.

Radiation and Cisplatin will be given concurrently and should start on the same day, \pm 1 day. Radiation will continue without interruption whenever possible. Radiation delays or interruptions will be the decision of the treating radiation oncologist, as outlined in section 5.3.

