10. STUDY CALENDAR

Baseline evaluations are to be conducted as follows:

- Within 3 weeks prior to registration: Complete history, physical examination, and evaluation of ECOG Performance Status, CBC; serum chemistry tests to include alkaline phosphatase, creatinine, electrolytes, AST (SGOT), and total bilirubin.
- All radiographic studies should be completed within:
 - Cohort 1: 6 weeks prior to registration
 - Cohort 2: 8 weeks prior to registration
- In the event that the patient's condition is deteriorating, laboratory evaluations should be repeated within 48 hours prior to initiation of the next cycle of therapy.

Pre-Study	Wk 1	Wk 2	Wk 3	Wk 4	Wk 5	Wk 6	Wk 7	Post Treatment Follow up	Long term Follow up ^b
Cisplatin Arm 1	A			A			A		
Cisplatin Arm 2	B	B	B	B	B	B	B		
Informed consent	X								
Demographics, medical history	X								
Concurrent meds		X ⁱ							
Physical exam	X	X		X			X	X	X ^h
Pulse, blood pressure	X	X		X			X	X	
Height	X								
Weight ^a	X	X	X ^a	X ^a	X	X ^a	X ^a	X	
Performance status	X	X						X	
CBC w/diff, plts ^a	X	X	X ^a	X ^a	X	X ^a	X ^a	X	X
Serum basic chemistry ^b			X ^a	X ^a		X ^a	X ^a		
Serum comprehensive chemistry ^c	X	X		X			X	X	
Adverse event evaluation		X-----							X
Tumor measurements	X ^d							X ^e	X ^e
B-HCG	X ^f								
Correlative studies		X							
FACTHN and FACT-COG ^g	X ^g						X ^g	X ^g	

A: Arm 1: Cisplatin 100 mg/m² every 3 weeks for 3 total doses

B: Arm 2: Cisplatin 40 mg/m² every week for 7 total doses

a: Every 3 weeks for Arm 1 during radiation, weekly for Arm 2 during radiation, and then as scheduled.

b: Weeks 2,3,5, 6 of Arm 2 only: creatinine, glucose, potassium, sodium.

c: Every three weeks for both arms: Albumin, alkaline phosphatase, total bilirubin, calcium, creatinine, potassium, SGOT [AST], SGPT [ALT], sodium.

- d: Baseline scans can include either: 1) CT with contrast or MRI of the head and neck region, CT of chest or chest x-ray. Response assessment should include assessment of all sites of disease and use the same imaging method as was used at baseline.
- e: Restaging scans must be repeated after the end of protocol treatment within 8 weeks of completion of radiation. Thereafter, scans of the head and neck will be repeated as clinically indicated, but at a minimum of every 6 months (± 6 weeks) for the first two years. Following this, all scans are at the treating physician's discretion.
- f: Serum pregnancy test (women of childbearing potential).

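### The catch-all toxicity rule in Section 6 stops radiation as well as cisplatin if read literally, which conflicts with Sections 5.2.1 and 5.3

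*Combined protocol and SAP*

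**What the plan says.** Section 6 lists eight toxicity-specific rules and then a catch-all. For any other event, nausea and vomiting excepted, the catch-all reads: "grade 3 or 4 non-hematologic toxicity not discussed above, hold all protocol treatment and discuss with the PI". It is not restricted to events attributed to cisplatin.

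Section 5.2.1 describes the planned treatment as radiation with one of two cisplatin schedules, beginning: "Treatment will consist of standard of care radiation therapy to the primary tumor of the head and neck". On continuity it says "Radiation will continue without interruption whenever possible", and on who decides, "Radiation delays or interruptions will be the decision of the treating radiation oncologist, as outlined in section 5.3". The opening of Section 5.3 adds that for radiation, "toxicities and dose modifications will be made by the treating physician based on institutional standards". Section 5.3.2 permits radiation breaks for severe acute toxicity or intercurrent illness.

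The pointers into Section 6 come from the cisplatin text. Section 5.2, on cisplatin administration, says "Appropriate dose modifications are described in Section 6", and Section 5.2.2 says "Please see Section 6.0 for all dose modifications of cisplatin". The heading over the dose-level table in Section 6 also names cisplatin only.

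**The concern.** Two instructions govern the same clinical moment and differ on what happens and who decides. The catch-all stops everything at once and brings in the PI. Sections 5.2.1 and 5.3 keep radiation going by default and give any interruption to the treating radiation oncologist or treating physician. The documents do not rank the two, and they do not define protocol treatment so as to leave radiation out.

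At stake is the continuity of curative-intent radiation. A clinician who follows Section 6 to the letter stops it. A clinician who follows Section 5 leaves the choice to the radiation oncologist. Two patients with the same event could be managed differently, each in line with some part of the protocol.

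**Working it through.** The plan gives no figure on this point, so the check compares the sections and makes two short counts.

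**1. Does the phrase include radiation?** The documents do not define protocol treatment. Section 5.2.1 makes radiation part of the planned treatment. Study calendar footnote e ties the end of protocol treatment to the end of radiation: "Restaging scans must be repeated after the end of protocol treatment within 8 weeks of completion of radiation". Cisplatin is the only drug under study, so the word *all* adds almost nothing unless radiation is meant. The literal reading includes radiation.

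**2. Is that likely to be what was meant?** The nine rules in Section 6 sort as follows.

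| What is held | Rules | Count |
|---|---|---|
| Cisplatin, by name | neutropenic fever; thrombocytopenia with bleeding; neurotoxicity; renal; mucositis; ototoxicity or tinnitus | 6 |
| Treatment, on a scheduled cisplatin day | neutropenia; thrombocytopenia | 2 |
| All protocol treatment | the catch-all | 1 |

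6 + 2 + 1 = 9. The section heading and both pointers into the section also concern cisplatin. The catch-all is the only exception.

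**3. Does the literal rule give sensible results?** Dysphagia has no rule in Section 6, so grade 3 dysphagia falls to the catch-all and radiation stops. Grade 4 mucositis has its own rule, which holds cisplatin only. The lower-grade event would then trigger the wider stop, which is hard to explain as a deliberate choice. Mucositis has a rule only at grade 4, so it is also unclear whether grade 3 mucositis counts as already covered.

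**4. What would a literal hold withhold?** Cisplatin days are taken from Section 5.2.2.

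- Arm 1: days 1, 22 and 43. The gaps are days 2–21 and days 23–42, each 20 calendar days.
- Arm 2: days 1, 8, 15, 22, 29, 36 and 43. The gaps are 6 days each.

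Radiation is the only treatment due inside a gap. A hold that begins and resolves within an Arm 1 gap therefore withholds radiation and no cisplatin.

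**5. How quickly would a hold matter for radiation compliance?** Section 5.3.2 counts an overall radiation time of up to 52 days as compliant. As an illustration, assume a Monday start, 35 fractions at 5 per week, and missed fractions added at the end. Seven weeks ending on a Friday finish on day 6 × 7 + 5 = 47. Days 48 and 49 are a weekend, so one missed fraction moves the end to day 50, three to day 52 and four to day 53. Four missed fractions exceed the limit. A 30-fraction course has more slack. The make-up provision in Section 5.3.2 names holidays and logistic reasons, not toxicity.

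**6. How many patients?** Section 5.3.3 expects grade 3–4 mucositis and/or dysphagia in about two-thirds of patients. That figure pools the two events and includes grade 4 mucositis, which has its own cisplatin-only rule. It shows that the trigger includes an expected radiation effect, but it cannot be turned into a count of patients affected.

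**The case against.** The strongest reply is that the text can be read without conflict. Protocol treatment is undefined, the plan repeatedly calls radiation standard of care, and Section 6 is a cisplatin section, so a reader in context may take the hold to mean cisplatin. Section 5.2.1 speaks specifically about radiation interruptions and can reasonably be taken to override a catch-all. The rule also requires a discussion with the PI, so a question could be settled quickly.

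Alternatively, the wording may be deliberate. A temporary full stop for an unanticipated grade 3–4 event is a plausible precaution, and Section 5.3.2 permits radiation breaks for severe acute toxicity.

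Part of this stands. The intent is an inference, and the disagreement is between an automatic stop and a clinician's decision, not over whether a break may ever occur. But the contextual reading has to set aside the plain words of a safety instruction, and no text says that Section 5.2.1 prevails. Discussion with the PI may shorten a hold but comes with the stop, not before it. The deliberate-precaution reading does not explain why grade 4 mucositis leaves radiation running.

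**Conclusion.** The concern holds, as a minor point. The conflict between Section 6 and Sections 5.2.1 and 5.3 is certain on the text. That the catch-all is the faulty side, and that a cisplatin-only hold was meant, is probable: it rests on the cisplatin scope of Section 6 and on the other eight rules.

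The defect is confined to one rule of nine. How often it would operate is unknown, because the documents give no rate for grade 3–4 dysphagia alone or for the other unlisted toxicities. The consequence also depends on clinicians applying the rule literally. It is a matter of trial conduct: no effect on sample size, power or the primary endpoint is shown.

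**What to change.** In the last rule of Section 6, replace the hold on all protocol treatment with: hold cisplatin and discuss with the PI; radiation interruptions remain the decision of the treating radiation oncologist per Sections 5.2.1 and 5.3. The triggering toxicities and the discussion with the PI stay as they are, and a radiation break for severe acute toxicity remains possible under Section 5.3.2.

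If the sponsor does want radiation to stop automatically, keep the rule and state the exception in Sections 5.2.1 and 5.3.

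The preferred change costs one sentence in a protocol amendment and adds no patients, visits or tests.
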